Study protocol and statistical analysis plan

The Efficacy of A New Crosslinked Hyaluronan Gel in the Prevention of Postoperative Intrauterine Adhesion After Dilatation and Curettage in Women With Delayed Miscarriage: A Prospective, Randomized, Controlled Trial

2016.05.09

Introduction

Intrauterine adhesions (IUAs) are defined as fibrous strings opposing walls of the uterus and/or cervix leading to partial or complete obliteration of the cavity. IUAs are frequently encountered in one out of five women after miscarriage. Trauma to a gravid uterine cavity is known to be the main cause of IUAs. Such trauma could be induced by uterine curettage in the postpartum period, after spontaneous miscarriage or during termination of pregnancy, or by cesarean section. After pregnancy, the uterus could be in a vulnerable state that making the basal layer of endometrium more easily damaged by any trauma, especially dilatation and curettage (D&C).

Study Objective

To evaluate the efficacy of a new crosslinked hyaluronan gel (Materegen[®]) in reducing intrauterine adhesions formation after D&C.

Study Design

Randomized controlled trial.

Study Site:

Six hospitals for maternal and child health care in China.

- Department of Obstetrics, Hunan Province Maternal and Child Health Care Hospital, Changsha, Hunan, China
- The Women's Health Center, Changsha Hospital for Maternal & Child Health Care, Changsha, Hunan, China
- Department of Obstetrics, The Maternal and Child Health Care Hospital of Hengyang City, Hengyang, Hunan, China
- Department of Obstetrics, The Maternal and Child Health Care Hospital of Changde City, Changde, Hunan, China
- Department of Obstetrics, Huaihua City Maternal And Child Health Care Hospital, Huaihua, Hunan, China
- Department of Obstetrics, Yueyang Maternal and Child Health-Care Hospital, Yueyang, Hunan, China

Statistical Analysis Site:

School of Medicine, The Third Xiangya Hospital of Central South University,

Changsha, Hunan, China.

Study Device:

A new crosslinked hyaluronan gel (MateRegen[®]), manufactured and supplied by BioRegen Biomedical (Changzhou, China), is a sterile, transparent, viscoelastic and non-pyrogenic gel composed of highly purified crosslinked hyaluronan molecules.

Participants:

Women undergoing dilatation and curettage for delayed miscarriage without previous dilatation and curettage. All participants were required to give their written, signed informed consent before participating.

The inclusion criteria:

- Patients to be female, aged 18-45 years
- Without previous dilatation and curettage
- Undergoing dilatation and curettage for the current delayed miscarriage
- All participants should be with normal liver/renal function and without systemic disease
- Agree to use adequate forms of contraception throughout the study
- Be in good compliance with the follow-up examination according to the study protocol

The exclusion criteria:

- Known/suspected intolerance or hypersensitivity to hyaluronan or its derivatives
- Genital tract malformation
- Inflammation of genital tract or pelvic cavity, clinical evidence of cancer in genital tract
- Suspected genital tuberculosis
- Abnormal blood coagulation
- Medical histories of peripheral vascular disease, alcohol/drug abuse, and mental illness
- Acute or severe infection
- Autoimmune diseases.

Trial Process Flow

Trail processes	Recruitment and Treatment		Follow-up
	Two weeks before surgery	Surgery	Three months after surgery (± 7 day)
Window period	X		
Informed consent form	X		
Inclusion/exclusion criteria	X		
Dropout criteria			X
General data	X		
Physical exam on vital signs	X		
Medical history	X		
Surgical history	X		
Diagnosis	X		
Surgery evaluation		X	
Medication		X	
AFS adhesion evaluation	X		X
Clinical symptoms and vital signs	X	X	X
AE		X	X
Randomization		X	
Device application		X	

Randomization and Interventions:

The participants were randomly assigned into group of either D&C alone (control group) or D&C plus intrauterine MateRegen[®] gel application (treatment group) in a 1:1 ratio; and the random sequences were generated by SAS[®] 9.13 (center stratified blocked randomization, block=10) (SAS Institute, Cary NC).

Surgical Procedure and Gel Application

All D&C procedures were performed by suction curettage under general anesthesia in accordance with procedural standards. At the end of the D&C procedure a syringe of MateRegen[®] gel (3ml) was applied to the uterine cavity for patients assigned to the treatment group through a 15-cm sterile delivery cannula, whereas nothing was applied to the uterine cavity for patients in the control group.

Follow-up and Measurement:

A follow-up hysteroscopic examination was scheduled 3 months (± 7 days) after the D&C procedure at about one week after the clean of menstrual bleeding. A pregnancy test was performed and before hysteroscopic examination. For patients with positive pregnancy test, the hysteroscopic examination was canceled.

Findings at follow-up hysteroscopy were evaluated and recorded according to the American Fertility Society (AFS) classification.

Table. The American Fertility Society (AFS) classification of intrauterine adhesion (1988)#

Extent of cavity involved	<1/3	1/3-2/3	>2/3
Score	1	2	4
Type of adhesions	Filmy	Filmy & dense	Dense
Score	1	2	4
Menstrual pattern	Normal	Hypomenorrhea	Amenorrhea
Score	0	2	4
Prognostic classification			
Disease severity	Cumulative score		
Stage I (mild)	1-4		
Stage II (moderate)	5-8		
Stage III (severe)	9-12		

#

Endpoints:

The primary endpoint was the number of women with formation of IUAs. The secondary endpoints included the adhesion scores of extent of uterine cavity involved, type of adhesion and menstrual pattern, the cumulative adhesion score and the severity of IUAs graded according to AFS classification. The safety was monitored based on the complications and adverse events recorded that was possibly related to the MateRegen[®] gel application.

Participant number

The primary hypothesis of this trial was to demonstrate the superiority of D&C plus MateRegen[®] gel over the D&C alone, with respect to the incidence of IUAs. The primary assumption was that the estimated incidence was 30% in control group and would be reduced to 15% by application of MateRegen[®] gel. With a 2-tailed 0.05 significance level and 20% loss rate during follow-up, 300 patients with 1:1 allocation would yield 80% power to detect the superiority.

Statistical analysis Plan

All randomized women who started treatment were included in analysis according to the intent-to-treat (ITT) principle. Continuous variables were expressed as mean \pm standard deviation (SD) or median \pm quartile range (QR). Categorical variables were described by counts and percentages. The student's t-test/Wilcoxon rank-sum non-parametric test and chi-square test/Fisher's exact test were used to check the homogeneity of baseline characteristics. The Wilcoxon rank-sum non-parametric test was used if variables do not follow the normal distribution and the results were expressed as median (Quartile Range) (QR). The Cochran-Mantel-Haenszel (CMH) Chi-Square test with center effect adjustment was performed to estimate the incidence difference between groups. The analysis of covariance with center effect adjustment was performed to estimate the difference of intrauterine adhesion scores between groups. All analyses were performed by using SAS[®] 9.13 (SAS Institute, Cary NC), and a $p \leq 0.05$ (two-tailed, $\alpha = 0.05$) was considered to be statistically significant.

#

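### A single fixed block of 10 per centre, printed in the protocol with no concealment described, makes up to one in six allocations predictable if a centre pools its past assignments; late opening and varied block lengths would close most of the gap

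*Combined protocol and SAP*

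**What the plan says.** Under Randomization and Interventions, women are allocated 1:1 from sequences generated in SAS, described as "center stratified blocked randomization, block=10". That is one fixed length, and it is printed in the protocol. Under Study Site there are "Six hospitals for maternal and child health care in China", so six separate sequences run.

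Under Surgical Procedure and Gel Application, the treatment arm is handled as follows: "At the end of the D&C procedure a syringe of MateRegen[®] gel (3ml) was applied to the uterine cavity". The control arm has no sham: "whereas nothing was applied to the uterine cavity for patients in the control group".

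In the table headed "Trial Process Flow", consent and the inclusion and exclusion criteria are marked in the column two weeks before surgery. Randomization is marked in the surgery column, with no order given relative to the curettage.

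The document does not say who holds the sequence, how an assignment is released, or whether the block length is withheld from sites.

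**The concern.** In a block of five and five, the rest of the block is fixed once one arm has used its five places. Concealment normally stops site staff from exploiting this, but none is described. The arms can be told apart at treatment, and the block length is in the protocol.

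Two things are at stake. First, a woman already enrolled could be moved up, put back or deferred according to the arm expected next. Second, the curettage could be done with the arm known or guessed. The second matters particularly here, because the Introduction gives trauma to the gravid uterus as the main cause of adhesions and singles out D&C. The operator's technique therefore acts directly on the primary endpoint. The CMH test adjusted for centre compares arms within each centre, so it cannot remove a difference in case order or technique that arises within a centre.

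**Working it through.** **The plan's own figure.** The document gives no figure for predictability. Its sample size reproduces and is not affected by this point. The inputs, from Participant number, are: "the estimated incidence was 30% in control group and would be reduced to 15% by application of MateRegen[®] gel", and "With a 2-tailed 0.05 significance level and 20% loss rate during follow-up".
- With pooled variance, n per arm = [1.960 × √(2 × 0.225 × 0.775) + 0.842 × √(0.30 × 0.70 + 0.15 × 0.85)]² / 0.15² = 120.5, so 121.
- Allowing for 20% loss, 121/0.8 = 151.25, so 152 per arm and 304 in total, against 300 stated.
- Power with 120 evaluable women per arm is 79.8%, against 80% stated.

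**Certain allocations, full pooling.** Inputs: block 10, 1:1, so m = 5 per arm and C(10,5) = 252 equally likely orders. The last k places are all forced when they all belong to one arm, which has probability 2 × C(10−k,5)/252. Summing over k = 1 to 5:
- 2 × (126 + 56 + 21 + 6 + 1)/252 = 420/252 = 1.667 per block. This equals 2m/(m+1) = 10/6.
- As a share, 1.667/10 = 16.7%. Over 300/10 = 30 complete blocks, 30 × 1.667 = 50 women, or about 8 per centre if the six recruit equally (assumption).
- Every block has at least one forced place. Two or more occur in 2 × 56/252 = 44.4% of blocks, and three or more in 2 × 21/252 = 16.7%.

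**Certain allocations, operators tracking only their own cases.** Assume that women in a centre are split at random and equally among k operators, and that each operator knows the block boundaries. A forced place is then certain to the treating operator only if all five women in the used-up arm were that operator's own cases, which has probability (1/k)⁵.
- Two operators: 16.7% × 1/32 = 0.52%, about 1.6 of 300.
- Three operators: 16.7% × 1/243 = 0.07%, about 0.2 of 300.

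**Best guess.** Always guessing the arm with more places left gives an expected m + ½ × [2¹⁰/252 − 1] = 5 + ½ × (4.063 − 1) = 6.53 correct per 10. That is 65.3%, against 50% by chance, and again assumes full pooling.

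**Varied block lengths.** These rows come from a simulation with 50 women per centre (assumed equal recruitment) and 3,000 runs. The observer knows the set of lengths and every past assignment.

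| Lengths | Certain in advance | Best guess right |
|---|---|---|
| 10 only | 16.7% | 65.3% |
| 8, 10, 12 | 1.4% | 64.6% |
| 6, 8, 10 | 1.7% | 65.9% |
| 4, 6, 8 | 2.2% | 67.7% |

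Varying the length removes nearly all of the certainty and hardly any of the above-chance guessing.

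**Smaller fixed blocks.** From 2m/(m+1) divided by 2m, which is 1/(m+1), the forced share is 33% for length 4, 25% for 6 and 20% for 8. A shorter fixed block would be worse.

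**The case against.** The strongest reply is that the one-in-six figure is conditional. It needs staff who know the block length and starting points and who pool every assignment in the centre. The document shows only that an operator sees the arm of the women that operator treats. It does not say that each centre has one operator, or that anyone kept a tally. A reader might infer that centres knew one in six allocations, or that each operator knew all past assignments; the text supports neither. This objection stands, and it is why 16.7% is given here as an upper case.

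The route to selection bias is also narrower than block predictability alone suggests. Consent and eligibility come before the day of randomization, so foreknowledge has less room to decide who is enrolled. Deferral and re-ordering remain possible.

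A further reply is that a block of 10 is already less predictable than shorter fixed blocks and keeps the arms balanced across six centres. That is true, but randomly varied lengths around 10 keep nearly the same balance without the certainty.

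Finally, performance bias depends more on when the assignment is opened than on block length. That is accepted, and late opening is put first in the fix. It does not cover the patient's or the hysteroscopist's knowledge of the arm, which is a separate matter.

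**Conclusion.** The point holds as a minor weakness in protection. The plan fixes one disclosed block length, describes no concealment, and does not say whether assignment comes before or after the curettage. Allocations certain in advance could be as many as 16.7% in expectation (about 50 of 300) with full pooling, known block boundaries and complete blocks. With two operators who track only their own cases the share is about 0.5%, and with three it is below 0.1%. The document does not show where between these limits the trial lies.

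A reader might go further in two ways. One is to conclude that bias occurred; nothing in the document shows that allocations were predicted or acted on. The other is to set 65.3% against 50% and credit varied blocks with closing that gap; they do not, since best-guess success stays at about 65%. The sample size and the planned analysis are unaffected.

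**What to change.** 1. State that each assignment is opened only after the curettage is complete, from a concealed list or central system that the operator does not hold. The gel is applied at the end of the procedure, so the arm is not needed sooner. This is the more direct guard against performance bias. It costs a sentence in the protocol and someone in theatre to obtain the assignment at that moment.
2. Generate each centre's sequence with randomly varied block lengths, for example 8, 10 and 12, and do not disclose the lengths to sites. This costs a change to the randomization program. The largest possible imbalance within a centre rises from 5 to 6 women (half the longest block).

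The two belong together. Opening late does not stop deduction from a fixed block, and varying the lengths does not help if the assignment is opened before the curettage. Together they still leave some above-chance guessing by anyone who pools past assignments.

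The protocol describes the sequences as already generated. If they are in use, apply the first change to all remaining women and the second to blocks not yet started.

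### Does the missing zero level in the AFS table leave women with a clear cavity without a score?

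*Combined protocol and SAP*

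**What the plan says.** The Endpoints section lists as secondary endpoints "the adhesion scores of extent of uterine cavity involved, type of adhesion and menstrual pattern", and then "the cumulative adhesion score and the severity of IUAs graded according to AFS classification". The AFS table under Follow-up and Measurement supplies the scoring. The row headed "Extent of cavity involved" gives 1, 2 or 4 points, and so does the row for type. Only menstrual pattern has a printed 0, for normal menses. Stage I covers totals of 1 to 4, Stage II 5 to 8 and Stage III 9 to 12.

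The Statistical analysis Plan opens with the analysis set: "All randomized women who started treatment were included in analysis according to the intent-to-treat (ITT) principle". It then compares adhesion scores between the groups by analysis of covariance adjusted for center. No sentence says how a woman with a clear cavity is scored, and none restricts the score analysis to women with adhesions. The Introduction defines an adhesion anatomically, as "fibrous strings opposing walls of the uterus and/or cervix leading to partial or complete obliteration of the cavity". The Trial Process Flow also lists "AFS adhesion evaluation" before surgery.

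**The concern.** Read literally, the table has no entry for the finding expected in most women. If a clear cavity has no extent or type score, it has no total and no stage, and the analyst must decide whether such women enter as 0 or drop out.

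That choice would matter. Over all women, the scores reflect both how often adhesions form and how bad they are. Among women with adhesions only, the comparison is of severity alone, in groups selected by outcome, and the protection of randomization is lost. The number analysed would fall from about 240 to about 54.

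A second worry arises if clear cavities do score 0 for extent and type. Hypomenorrhea alone then totals 2 and amenorrhea alone totals 4. Both lie in the Stage I range although no adhesion was seen.

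**Working it through.** **Inputs** (Participant number section): adhesion incidence 30% in the control arm and 15% in the gel arm, two-sided 0.05, 80% power, and "20% loss rate during follow-up, 300 patients with 1:1 allocation".

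**1. The plan's sample size.** With pooled variance under the null and mean proportion 0.225:

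n = [1.960 × √(2 × 0.225 × 0.775) + 0.842 × √(0.30 × 0.70 + 0.15 × 0.85)]² / 0.15² = 121 per arm after rounding up.

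Two arms need 242, and 242 / 0.80 = 303, close to the stated 300. With 120 examined per arm the power is 79.8%. The stated figure reproduces, and the AFS score plays no part in it.

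**2. Expected clear cavities.** 300 × 0.80 = 240 examined, 120 per arm.
- Control: 120 × 0.70 = 84 clear, 36 with adhesions.
- Gel: 120 × 0.85 = 102 clear, 18 with adhesions.
- Together: 186 of 240 = 77.5% clear, 54 with adhesions.

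If the gel had no effect and both arms were at 30%, the count would be 2 × 84 = 168 of 240.

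**3. Totals the table allows.** With an adhesion, extent (1, 2, 4) plus type (1, 2, 4) plus menses (0, 2, 4) gives 2 to 10, or 12. With extent and type at 0, the total is 0, 2 or 4, depending on menses alone.

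**4. Three ways to treat a clear cavity.** Let m be the mean cumulative score among women with adhesions, assumed equal in both arms, with normal menses in clear cavities. Control minus gel is then:

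| Treatment of a clear cavity | Difference | m = 2 | m = 5 |
|---|---|---|---|
| Scored 0, all women kept | 0.30m − 0.15m = 0.15m | 0.30 | 0.75 |
| Left out (36 vs 18) | m − m = 0 | 0 | 0 |
| Lowest printed levels, 1 + 1 | 0.15(m − 2) | 0 | 0.45 |

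The choice changes the answer, so what counts is which treatment the text supports. The third records a filmy adhesion over less than a third of the cavity in a woman who has none, which contradicts the finding itself. The second needs a restriction that appears nowhere and that conflicts with the stated analysis set. Only the first fits.

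**5. Menstrual points in clear cavities.** Suppose a proportion q of clear-cavity women in each arm has hypomenorrhea (2 points). The documents give no value for q or m; m = 4.5 is an assumed mild mix of scores.
- Control mean = 0.30m + 0.70 × 2q; difference = 0.15m − 0.15 × 2q = 0.15(m − 2q).
- q = 0: 0.675 / 1.35 = 50% reduction.
- q = 0.10: 0.645 / 1.49 = 43%.
- q = 0.20: 0.615 / 1.63 = 38%.

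Simulated power for the cumulative score under this mix is 71%, 67% and 63%. Counting the points dilutes the cumulative score modestly. It leaves the extent and type scores untouched and treats both arms alike.

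**The case for a change.** The best case for a change is that the table takes the trouble to print a 0 for normal menses and prints none for extent or type, and that citing a published scale is not an analysis rule. The phrase about the severity of adhesions could be read as applying only to women who have them. The stakes between the two populations can be made to look large: the detectable difference at 80% power is 0.363 SD with 120 vs 120 and 0.826 SD with 36 vs 18. If gel-arm adhesions were the more severe (assumed means 5.9 and 4.5), gel minus control would be 0.15 × 5.9 − 0.30 × 4.5 = −0.465 over all women but 5.9 − 4.5 = +1.4 among those with adhesions.

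The omission stands as a fact. The consequences do not, because they measure a restricted analysis that the SAP does not describe, and the reversal of sign needs a severity pattern that nothing in the documents suggests. The zero difference among women with adhesions follows directly from assuming equal severity.

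On staging, the conditional wording helps the plan. If severity belongs to an adhesion, and an adhesion is anatomical, a clear cavity with light menses is outside the stages. At an assumed 10% with abnormal menses, about 84 × 0.10 = 8 control and 102 × 0.10 = 10 gel women would be concerned, and they would be reported as having no adhesion.

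The pre-surgery evaluation adds little. The table is tied to follow-up hysteroscopy, and the same zero would serve before surgery.

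One matter is left over: women who are never examined have no score, although the analysis set includes them. That is a missing-data question, and a zero level for clear cavities would not settle it.

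**Conclusion.** This is a gap that a competent analyst fills sensibly, and no change to the plan is needed. The table omits a line for a clear cavity, which on the plan's rates would describe about 186 of 240 examined women. But the analysis set, the comparison between arms and a lowest stage starting at 1 all lead to the same rule: 0 for extent and type, with the woman kept in the comparison. The wording of the severity endpoint, with the anatomical definition of an adhesion, keeps women without one out of the stages.

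Writing the rule down would be tidy, but it would change neither who is analysed nor how they are scored. What remains open is whether menstrual points in clear cavities count towards the cumulative score. Under the assumed mild mix, counting them costs about 4 to 8 points of power on one secondary endpoint (71% to 67% or 63%).

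The conclusion rests on the plan's own 30%, 15% and 20% for the counts, and on the table being complete as read. Its title carries a footnote mark whose text did not survive, so a scoring note cannot be excluded; such a note could make the gap smaller still. The primary endpoint and the 300 women are unaffected.

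### Safety is tied to events judged related to a gel that controls never receive, and no comparison of all events by arm is stated

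*Combined protocol and SAP*

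**What the plan says.** All references are to the combined protocol and SAP.

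- **Endpoints:** one sentence deals with safety: "The safety was monitored based on the complications and adverse events recorded that was possibly related to the" gel application. No other safety measure is defined.
- **Surgical Procedure and Gel Application:** in the comparison arm, "nothing was applied to the uterine cavity for patients in the control group". There is no sham or placebo device, and blinding is not described anywhere.
- **Trial Process Flow:** the AE row is marked at surgery and at the three-month visit. The row "Clinical symptoms and vital signs" is marked in all three columns. Neither row is restricted by arm or by relatedness.
- **Statistical analysis Plan:** the analysis set is given by "All randomized women who started treatment were included in analysis according to the intent-to-treat (ITT) principle". The descriptive rule is "Categorical variables were described by counts and percentages". The between-group methods are baseline homogeneity tests, a CMH "test with center effect adjustment was performed to estimate the incidence difference between groups", and analysis of covariance for adhesion scores. Adverse events, complications and safety are not mentioned.
- **Study Objective:** the only aim is "To evaluate the efficacy of a new crosslinked hyaluronan gel" in reducing adhesions.

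**The concern.** Every woman in the trial has suction curettage under general anesthesia, so an event such as bleeding or infection can occur with or without the gel. The randomised control arm shows how often such events occur without gel. The safety sentence does not call on it. It relies on someone deciding, event by event, whether the gel might be responsible.

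With no sham and no blinding described, that decision may be made with the arm known. It can go wrong in two directions. Events attributed to the curettage could conceal a real excess with gel, and background events attributed to the gel could suggest an excess that does not exist. If relatedness is applied as a filter, the reader sees a gel-arm count with nothing to set it against.

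**Working it through.** **1. Whether control events can qualify.** The safety sentence can be read in three ways.

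| Reading of the relatedness qualifier | Can control events count? | All events in both arms stated? |
|---|---|---|
| Applies to complications and adverse events alike (natural reading) | No: a woman given no gel cannot have an event related to its application | No |
| Applies to adverse events only | Complications yes, adverse events no | No |
| Describes types of event the gel could cause | Yes, for those types | No |

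The Statistical analysis Plan does not choose between these readings, because it never mentions adverse events.

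**2. The numbers per arm.** The plan gives no safety figure. Its only related figure is the total of 300 (Participant number: 30% versus 15%, two-sided 0.05, 80% power, 20% loss, 1:1).

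- Pooled-variance formula: n = [1.96·√(2·0.225·0.775) + 0.8416·√(0.30·0.70 + 0.15·0.85)]² / 0.15² = 120.5, so 121 per arm. Then 121/0.8 = 151.25, so 152 per arm and 304 in total.
- Unpooled formula: 118 per arm, then 118/0.8 = 147.5, so 148 per arm and 296 in total.
- Power with 120 evaluable women per arm is 79.8%.

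The figure of 300 therefore reproduces. It gives 150 per arm randomised, and 150 × 0.8 = 120 per arm after the planned loss.

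**3. What the filtered count conveys.** All rates here are assumptions. On the natural reading the reported count is 150 × p_gel × f, where f is the fraction judged possibly related. With p_gel = 10%, f = 25%, 50% or 100% gives 3.75, 7.5 or 15 women. The control rate does not enter the formula, so the count is unchanged by it. That follows by construction and is not an empirical finding. It shows only what a filtered count leaves out.

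For comparison, an all-event table would give RD ± 1.96·√[p_gel(1−p_gel)/n + p_ctl(1−p_ctl)/n]. With p_gel = 10% and n = 150:

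| Assumed control rate | Expected women, gel vs control | Risk difference, points (95% CI) |
|---|---|---|
| 5% | 15 vs 7.5 | +5.0 (−0.9 to 10.9) |
| 10% | 15 vs 15 | 0.0 (−6.8 to 6.8) |
| 20% | 15 vs 30 | −10.0 (−18.0 to −2.0) |

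These three situations are distinguishable in a by-arm table and identical in the filtered count. With 120 per arm, the first interval widens to −1.6 to 11.6.

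**4. Precision of a by-arm comparison.** With a common rate p, the half-width is 1.96·√(2p(1−p)/n).

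| Assumed common rate | n = 150 per arm | n = 120 per arm |
|---|---|---|
| 5% | 4.9 points | 5.5 points |
| 10% | 6.8 points | 7.6 points |
| 20% | 9.1 points | 10.1 points |

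**The case against.** The strongest reply is that the plan does not exclude the control arm. It says that safety was monitored, and its loose wording allows readings under which some control events count. General rules could also be stretched to produce a by-arm table: the analysis set covers all randomized women who started treatment, categorical variables get counts and percentages, and the CMH sentence refers to an incidence difference without limiting it to adhesions. The only objective is efficacy, and no safety test is promised.

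Much of this stands. A reader might infer that the control arm is barred from safety interpretation, or that adverse events are not collected in controls. The documents support neither inference. The exact claim is that no planned use of the control arm for safety is stated.

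The general rules do not close the gap, however. The CMH sentence most likely means adhesions, since Participant number uses incidence in that sense. The descriptive rule does not say which events are counted, or that they are counted regardless of attribution.

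Two cautions about the remedy also stand. The flow table does not distinguish the arms at all: it marks device application without restriction too, although controls receive none. It therefore makes adverse event collection in both arms plausible but does not prove it. And intervals based on 150 per arm assume complete follow-up, which the plan itself does not expect.

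**Conclusion.** The point holds as a defect in the safety definition and its analysis. The one stated rule, followed as written, yields a count filtered by judged relatedness with no interpretable comparator, and no reading of the text commits to comparing all events by arm. It should be corrected because a criterion listed under Endpoints ought to be interpretable.

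Its size cannot be measured from the documents, which give no event rates; the scenario figures are illustrations only. The point does not go so far as to say that control data go uncollected, that the analysis set is wrong, or that a formal safety test was owed. The efficacy conclusion does not change.

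**What to change.** Under Endpoints, define safety as all complications and adverse events recorded from D&C to the three-month visit in both arms, regardless of attribution.

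In the Statistical analysis Plan, add that these events are tabulated by arm in all randomized women who started treatment, which is the set already named. Give counts, percentages and a risk difference with 95% CI, labelled descriptive. State how many women in each arm lacked the three-month visit, so that the denominators can be judged. Keep judged relatedness as a secondary description.

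The cost is one endpoint sentence, one SAP sentence and a table or two. No new visits, patients or data should be needed, provided the AE schedule is applied to both arms; the plan should say that it is. The downside is imprecision. The trial was not sized for safety, and the half-widths worked out above mean that the table describes and does not test.

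### Does planning on a 30% control incidence, when the Introduction cites one in five after miscarriage, undermine the stated 80% power?

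*Combined protocol and SAP*

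**What the plan says.** Under Participant number, the plan sets its rates in one sentence, "The primary assumption was that the estimated incidence was 30% in control group and would be reduced to 15% by application of" the gel, and then gives the operating characteristics: "With a 2-tailed 0.05 significance level and 20% loss rate during follow-up", "300 patients with 1:1 allocation would yield 80% power to detect the superiority". No source for 30% is cited, and the plan does not say whether the effect is meant as a halving or as a 15-point drop.

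The Introduction carries the only other incidence figure: "IUAs are frequently encountered in one out of five women after miscarriage". It names trauma to the gravid cavity as the main cause of adhesions and picks out dilatation and curettage (D&C) as a particular hazard to the basal endometrium after pregnancy.

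The inclusion criteria require that women be "Without previous dilatation and curettage", and also that they be having the procedure now for the current delayed miscarriage.

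**The concern.** A reader who meets 20% in the Introduction and 30% in the sample-size paragraph will ask why the larger figure was used, because a higher control rate makes a halving easier to detect. Nothing in the document links the two numbers. Restricting entry to women with no earlier curettage also seems to remove one reason for expecting a rate above the background.

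If 20% were the right control rate and the gel halved it, the trial would miss that effect about 41% of the time rather than the advertised 20%. A non-significant result might then be taken as evidence that the gel does not work. The design also has no reserve: for a halving, 80% power needs a control rate of about 30.1%.

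**Working it through.** **Inputs.** All are from Participant number unless noted.
- Two-sided α = 0.05, so z = 1.960. Target power 80%, so z = 0.842.
- 300 women at 1:1 is 150 per arm. With 20% loss, 150 × 0.8 = 120 examined per arm.
- Planned rates p₁ = 0.30 (control) and p₂ = 0.15 (gel).
- Alternative control rate 0.20 (Introduction). Halving it to 0.10 is an assumption, since the plan does not fix the effect scale.
- The planned test is a centre-adjusted Cochran-Mantel-Haenszel chi-square. It is approximated here by the unstratified chi-square without continuity correction; stratification should change power little.

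**Formulas**, with p̄ = (p₁ + p₂)/2 and d = p₁ − p₂:

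n per arm = [1.960·√(2p̄(1−p̄)) + 0.842·√(p₁(1−p₁) + p₂(1−p₂))]² / d²

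power = Φ{ [d·√n − 1.960·√(2p̄(1−p̄))] / √(p₁(1−p₁) + p₂(1−p₂)) }

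**Step 1: the plan's own figure.** For 30% v 15%, p̄ = 0.225, √(2 × 0.225 × 0.775) = 0.5906 and √(0.21 + 0.1275) = 0.5809.
- n = (1.1575 + 0.4889)² / 0.0225 = 120.5, so 121 per arm. Then 121/0.8 gives 152 per arm, or 304 in total. The unpooled and arcsine formulas give 118 and 119 per arm, or about 296–298 in total. The stated 300 sits among these.
- Power at n = 120: (1.6432 − 1.1575)/0.5809 = 0.836, and Φ(0.836) = 79.8%. The exact binomial value is 80.5%.

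The stated 80% is reproduced.

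**Step 2: a 20% control rate, halved.** For 20% v 10%, √(2 × 0.15 × 0.85) = 0.5050 and √(0.16 + 0.09) = 0.5.
- Power at n = 120: (1.0954 − 0.9897)/0.5 = 0.211, and Φ(0.211) = 58.4% (exact 59.3%).
- For 80% power: (0.9897 + 0.4208)² / 0.01 = 199 per arm. Then 199/0.8 = 249 per arm, or 498 in total.

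**Step 3: both sides of 30%, and both effect scales** (120 per arm, pooled formula):

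| Control | Gel | Power |
|---|---|---|
| 20% | 10% (halved) | 58.4% |
| 25% | 12.5% (halved) | 70.1% |
| 30% | 15% (planned) | 79.8% |
| 32% | 16% (halved) | 83.1% |
| 35% | 17.5% (halved) | 87.4% |
| 20% | 5% (15 points kept) | 94.5% |

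At a 20% control rate, any gel rate of about 7.6% or lower gives at least 80% power. Holding the absolute difference at that control rate moves power up; holding the relative difference moves it down.

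**Step 4: do the two rates refer to the same women?** The Introduction's sentence covers women after miscarriage, with no restriction on how the miscarriage was managed. The trial's controls all have a curettage. Since the Introduction treats that procedure as especially harmful to the endometrium, a rate above the general figure fits the document's own reasoning. Excluding earlier curettage removes one source of extra risk and leaves the present procedure untouched. The document gives no separate curettage-specific rate, so it neither confirms nor refutes 30%.

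**The case for a change.** The strongest case for acting is that 30% is unsupported on paper, that the only other figure is lower, and that even a midpoint of 25% costs about 9 points of power. A halving is also the relative effect the plan itself specifies, whereas holding 15 points at a 20% control rate would mean a 75% relative reduction that the plan nowhere claims. Stating power as a range and saying how a null result will be read would cost only wording.

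Much of this stands as description: the rate is unsourced, and the 58–59% is correct under its two conditions. It does not stand as a fault. Any power statement depends on its inputs, and these are set out openly. A table confined to control rates of 30% and below would be one-sided. Nothing in the plan says that a non-significant result will be read as absence of effect. The analysis is already directed at estimating the incidence difference, so an analyst would report it with its confidence interval, which shows what the data can exclude whatever control rate was assumed beforehand.

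Cancelled hysteroscopies after a positive pregnancy test might add to the loss. The documents give no figure for this, participants must agree to use contraception, and the 20% allowance can be read as including such cases.

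**Conclusion.** No change is called for. The 80% power with 300 women is correct for 30% v 15% with 20% loss (79.8% by formula, 80.5% exact). The drop to 58–59% needs two conditions together: a control rate of 20% in women who all undergo curettage, and an effect of exactly one half. The documents establish neither. Other readings within the same document give power from about 70% to 94%.

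The remaining gap is that 30% has no citation and is not related to the one-in-five figure. Supplying that would be a courtesy to the reader. It would leave the sample size, primary test, endpoint and stated power as they are. This conclusion assumes 120 examined women per arm and an uncorrected chi-square as a stand-in for the centre-adjusted test.
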